1.2 Inclisiran, an siRNA Therapeutic for Hypercholesterolemia

[figure not shown]
Inclisiran sodium is a chemically synthesized siRNA double-stranded oligonucleotide, covalently linked to a ligand containing three GalNAc residues.

Inclisiran is a long-acting, subcutaneously delivered, synthetic siRNA directed against PCSK9 that is conjugated to triantennary GalNAc carbohydrates. These carbohydrates bind to abundant liver-expressed asialoglycoprotein receptor, leading to inclisiran uptake specifically into hepatocytes.

When introduced into the hepatocyte, inclisiran engages the natural pathway of RNAi by binding intracellularly to the RNA-induced silencing complex (RISC), enabling it to cleave mRNA molecules encoding PCSK9 specifically. The cleaved PCSK9 mRNA is degraded and thus unavailable for protein translation, which results in decreased levels of the PCSK9 protein. A single siRNA-bound RISC is catalytic and cleaves many transcripts and the duration of action is anticipated to be longer than other mechanisms.

1.2.1 Nonclinical Studies

Inclisiran was specifically designed with molecular and biochemical characteristics to minimize untoward side effects which are reflected by the absence of dose limiting toxicities in preclinical models. For example, GalNAc ligands were added to the RNA strands in order to target inclisiran to receptors on hepatocytes, thereby greatly reducing uptake by heterologous tissue. This is highlighted by tissue distribution studies in rats showing that compared to liver, inclisiran exposure in other tissues was 36-fold to 1076-fold lower than liver. [REDACTED]

Inclisiran was well tolerated in all studies. The most common findings were related to the expected pharmacological effects of inclisiran on lipid profiles and histopathological findings of vacuolation in hepatocytes of rats and lymph node macrophages of monkeys and the presence of basophilic granules in hepatocytes of monkeys and kidneys of rats. These microscopic findings are not considered adverse because they are not associated with changes in clinical pathology parameters. Liver function enzymes were only minimally to mildly increased, and were reversible following treatment-free periods, and there were no changes in urinalysis or urine chemistry parameters.

Additional non-clinical studies are ongoing or planned.

1.2.2 Clinical Studies

1.2.2.1 Clinical pharmacology

Inclisiran is inactive in plasma and acts directly in the hepatocytes leading to inhibition of PCSK9 protein synthesis. After SC administration of inclisiran, peak plasma concentrations were observed by 4 hours and became undetectable in plasma in 24 hours to 48 hours with an elimination terminal half-life ($t_{1/2}$) of 7.3 hours and dose-proportional increase in exposure parameters of maximum plasma concentration (C_{max}) and area under the curve (AUC). There was no accumulation of inclisiran plasma concentrations following multiple weekly, biweekly or monthly dosing. Mean fraction excreted unchanged in the urine was around 25%. In vitro studies using hepatic P450 metabolic enzymes showed that inclisiran neither inhibited nor induced common hepatic metabolic pathways.

In a Phase I study in subjects with renal impairment (ORION-7, also referred to as CKJX839A12103) ([Section 1.2.2.2.4](#)), a single 300 mg SC dose of inclisiran sodium which is equivalent to 284 mg inclisiran was observed to increase C_{max} and AUC up to approximately two-fold in subjects with mild and moderate renal impairment, and increased C_{max} up to four-fold and AUC up to three-fold in subjects with severe renal impairment compared to subjects with normal renal function. However, by 48 hours plasma levels of inclisiran were below the level of quantification in all groups.

Despite the differences observed in pharmacokinetic (PK) parameters over the first 48 hours following injection of inclisiran, there were generally no relevant differences between the groups with respect to PCSK9 reduction and LDL-C reduction. In addition, there was no difference in the overall safety profile between subjects with normal renal function and those with mild, moderate, or severe renal impairment.

This finding is consistent with that observed in the previous Phase I (ALN-PCSSC-001, also referred to as CKJX839A12101.) study ([Section 1.2.2.2.1](#)) where doses above 300 mg, which is

equivalent to 284 mg inclisiran, led to a dose related increase in PK parameters. A single 500 mg dose increased AUC two to three fold and C_{max} four to five fold compared to a single 300 mg dose, which is similar to the increase observed in subjects with severe renal impairment compared to those with normal renal function in this study. In both the Phase I (ALN-PCSSC-001) and Phase II (ORION-1 also referred to as CKJX839A12201) studies single doses above 300 mg did not lead to greater reductions in PCSK9 or LDL-C levels over time or differences in the safety profile.

These data support the administration of inclisiran to subjects with mild, moderate, or severe renal impairment in future and ongoing clinical studies with inclisiran.

Additional clinical pharmacology studies are ongoing or planned.

1.2.2.2 Clinical

Results are presented from four clinical studies:

1.2.2.2.1 Study ALN-PCSSC-001 (also referred to as CKJX839A12101)

ALN-PCSSC-001 (completed) was a Phase I study in which single (25 mg, 100 mg, 300 mg, 500 mg and 800 mg) and multiple [125 mg once weekly (four doses), 250 mg every 2 weeks (two doses), 300 mg every 4 weeks (two doses) and 500 mg every four weeks (two doses)] doses of inclisiran sodium were evaluated. Subjects in this study were followed until their LDL-C levels returned to $\geq 80\%$ of the baseline value or until 180 days after the last dose was given, whichever occurred first. At cumulative doses of 100 mg or greater, the majority of subjects reached 180 days of follow-up after the last dose, confirming the extended duration of action of inclisiran. No further follow-up occurred beyond this time point in this Phase I study. All adverse events (AEs) were mild or moderate (Grade 1 or 2) in severity with no differences relative to placebo other than skin reactions which were infrequent, mild and reversible following inclisiran.

The Phase I study demonstrated that the 300 mg dose of inclisiran sodium administered as a single or multiple dose is the lowest dose to achieve near-maximal reductions in PCSK9 and LDL-C levels. Two 300 mg doses of inclisiran sodium given 30 days apart achieved an additional 10% LDL-C reduction compared to a single 300 mg dose. PK parameters of inclisiran demonstrated a short plasma half-life ($t_{1/2} = \sim 6$ hours) and did not correlate with the observed pharmacodynamic (PD) effects of inclisiran.

1.2.2.2.2 Study ORION-1 (MDCO-PCS-15-01 also referred to as CKJX839A12201)

ORION-1 (MDCO-PCS-15-01, completed study) was a Phase II, double-blind, randomized, multi-national, multi-center study in subjects with ASCVD or ASCVD-risk equivalents (eg, diabetes and FH) and elevated LDL-C despite maximum tolerated dose of LDL-C lowering therapies to evaluate the efficacy, safety, and tolerability of inclisiran injection(s).

A total of 501 subjects were randomized to a single dose regimen of placebo, 200 mg inclisiran sodium, or 300 mg inclisiran sodium, 500 mg inclisiran sodium (on Day 1) or a double-dose regimen of placebo, 100 mg inclisiran sodium, 200 mg inclisiran sodium, or 300 mg inclisiran sodium (on Day 1 and Day 90).

The 300 mg dose provided near maximal PCSK9 and LDL-C reductions. The 500 mg dose did not provide a meaningful further increase in PD effect. The double-dose regimen of 300 mg regimen led to reduced LDL-C of 52.6% (LS mean) compared to a 1.8% increase in the placebo

group ($p < 0.0001$) at Day 180. Similarly, this regimen led to reduced PCSK9 of 69.1% (mean) compared to a 1.2% decrease in the placebo group at Day 180. At Day 360 (9 months after the second 300 mg dose), LDL-C reduction was 33.8%.

There were no clinically significant safety observations other than mild-moderate, short-lived skin reactions at the injection site in approximately 5% of subjects. Local injection site reactions were not dose-related.

1.2.2.2.3 Study ORION-2 (MDCO-PCS-16-02, also referred to as CKJX839A12202)

ORION-2 (MDCO-PCS-16-02 completed study) was a Phase II, open label, single arm, multicenter pilot study in subjects with homozygous familial hypercholesterolemia (HoFH). Four subjects were randomized and received open-label inclisiran sodium 300 mg SC on Day 1. The subsequent dosing interval was determined by PCSK9 level at Day 60 or 90 or rate of change of PCSK9 between Days 60 and 90. In three subjects mean serum PCSK9 levels were not suppressed by $>70\%$ at Day 60 or 90, as compared to baseline and received a second injection on Day 90.

Inclisiran treatment resulted in robust and durable reductions in PCSK9 levels in all four subjects treated at a dose of 300 mg SC. Three of the four subjects also had significantly reduced levels of LDL-C. One subject had a significant reduction in PCSK9 but not a concomitant reduction in LDL-C. The mean percentage LDL-C reduction from baseline was 12.3% and 21.0% at Day 90 and Day 180, respectively. The maximum reductions in LDL-C were at Day 120 for two subjects and at Day 150 for a third subject. Therefore, the second dose achieved a greater reduction in LDL-C than after the first dose.

The mean percentage PCSK9 reduction from baseline was 59.0% and 62.9% at Day 90 and Day 180, respectively. Decreases in other lipids, lipoproteins, and apolipoproteins were commensurate with the decreases in LDL-C.

No safety observations were noted and inclisiran was generally well tolerated. Three of the four subjects reported adverse events. None were considered related to study drug and the majority have resolved. One adverse event of leg pain was not resolved at the most recent visit. There were no deaths and one SAE (unstable angina, which was not considered related to study drug). No subjects withdrew due to an adverse event and no adverse events at the injection site were reported.

Elevations in chemistry parameters were observed. One subject with an elevated total bilirubin ($>1x$ ULN) at screening experienced a single elevation of total bilirubin $>2x$ ULN on Day 120. There were no ALT or AST elevations $>3x$ ULN or CK elevations $>5x$ ULN. [REDACTED]

The results from this pilot study support the 300mg dose and dose regimen for the ongoing Phase III ORION-5 study in HoFH.

1.2.2.2.4 Study ORION-7 (MDCO-PCS-16-03, also referred to as CKJX839A12103)

ORION-7 (MDCO-PCS-16-03); completed study) was a Phase I, single-dose, open-label study to evaluate the PK, safety, and PD of a single dose of inclisiran sodium 300 mg, SC injection in subjects with renal impairment compared to subjects with normal renal function. Subjects were classified into one of four renal function groups (normal, mild, moderate, and severe), as defined

by creatinine clearance (CrCl) which was calculated using the Cockcroft and Gault estimation from a spot serum creatinine level (Table 1-1).

Table 1-1 Renal Function Categories by Estimated CrCl Ranges

Group	Description	Estimated CrCl (mL/min)
1	Normal renal function	≥ 90
2	Mild renal impairment	60 to 89
3	Moderate renal impairment	30 to 59
4	Severe renal impairment	15 to 29

CrCl=creatinine clearance

These subjects were matched for age (+/- 10 years), body weight (+/- 20%), and proportional race and gender in order to ensure that the normal renal function group was comparable to the renal impairment groups for average demographics. Thirty-one subjects were randomized into the study, eight subjects in each of the normal renal function and the mild and moderate renal impairment groups and seven in the severe renal impairment group. All subjects completed the study to Day 60.

In individuals with mild, moderate and severe renal impairment, inclisiran C_{max} was 2.33, 1.97 and 3.31 fold higher, respectively; AUC₀₋₂₄ was 1.75, 1.91 and 2.50 fold higher, respectively; AUC₀₋₄₈ was 1.58, 1.83 and 2.33 fold higher, respectively; AUC_{0-t} was 1.53, 1.73 and 2.35 fold higher, respectively; AUC_{0-inf} was 1.44, 1.39 and 2.23 fold higher, respectively, relative to subjects with normal renal function. However, inclisiran was not detectable in plasma 48 hours after administration of a single 300 mg dose in any group irrespective of renal impairment.

At Day 60, LDL-C (beta-quantification) was reduced by 57.56%, 35.11%, 53.09%, and 49.20%, in the normal renal function group and the mild, moderate, and severe renal impairment groups respectively. Mean LDL-C reduction was less in the mild renal impairment group compared to the other three groups. Overall, LDL-C reduction was generally similar between groups with no impact of renal function on LDL-C response.

A single injection of 300 mg inclisiran was generally well tolerated in all study groups with no clinically significant safety findings to date. There was no difference in the overall safety profile between subjects with normal renal function and those with mild, moderate, or severe renal impairment and therefore no dose adjustment of inclisiran is considered necessary in subjects with renal impairment.

1.3 Known and Potential Risks and Benefits

Subjects taking part in this clinical study will receive guideline recommended standard of care as background therapy (including maximally-tolerated statin therapy and/or other LDL-C lowering therapies) when administered inclisiran. Reduction of LDL-C has been associated with reduced CV risk both by epidemiology and in controlled clinical trials. Injection site reaction is the only event known to be attributed to inclisiran treatment. The safety profile of inclisiran observed to date is considered acceptable for this clinical trial.

An expanded risk-benefit summary is provided in the current/approved version of the investigator brochure (IB).

1.4 Study Rationale

1.4.1 Study Rationale

The overall safety data from inclisiran in nonclinical studies and clinical data from the Phase I and Phase II study (ORION-1 also referred to as CKJX839A12201), and multiple PCSK9 antibody studies demonstrated that potent lowering of PCSK9 is well tolerated in human subjects and support the dose and dosing schedule proposed in this Phase III extension study. This extension study allows subjects continued access to inclisiran treatment and to allow the collection of additional efficacy and safety beyond the end of the original studies.

1.4.2 Dose Rationale

Previous studies have shown that a 300 mg dose of inclisiran sodium is well tolerated and provides maximum efficacy (ie, doses higher than 300 mg did not provide additional efficacy in LDL-C lowering). Subjects completing the Phase II trial MDCO-PCS-16-01 (ORION-3, also referred to as CKJX839A12201E1) or one of the Phase III lipid lowering studies [MDCO-PCS-17-03 (ORION-9, also referred to as CKJX839A12303), MDCO-PCS-17-04 (ORION-10, also referred to as CKJX839A12304) or MDCO-PCS-17-08 (ORION-11, also referred to as CKJX839A12305)] and fulfilling all inclusion and exclusion criteria of this study will receive inclisiran sodium 300mg at the next time point they are scheduled as per the previous study to receive inclisiran i.e. 180 days after the last injection in the previous study. Modelling and simulation has demonstrated that this regimen will allow for the necessary robust and sustained reduction in PCSK9 (and LDL-C) and has the potential to tackle the lack of adherence generally seen in the chronic management of subjects with hypercholesterolemia. The 300 mg dose of inclisiran sodium will be used for the entire duration of this study for subjects receiving inclisiran.

1.5 Study Population

This study will include male or female subjects who have completed a previous qualifying Phase II lipid lowering trial [MDCO-PCS-16-01 (ORION-3)] or Phase III lipid-lowering ORION feeder study [MDCO-PCS-17-03 (ORION-9), MDCO-PCS-17-04 (ORION-10) or MDCO-PCS-17-08 (ORION-11),], and fulfill the study entry criteria.

2 Study Objectives and Purpose

2.1 Primary Objectives

The primary objectives of the study are to evaluate:

- The effect of inclisiran treatment on the proportion of subjects achieving prespecified LDL-C targets at end of study (EOS)
- The safety and tolerability profile of long-term use of inclisiran

2.2 Secondary Objectives

The secondary objectives of this study are to evaluate the effect of inclisiran on:

- LDL-C levels
- Other lipids and lipoproteins

3 Study Design

3.1 Type/Design of Study

[figure not shown]
This study will be a long-term extension of the Phase II lipid lowering trial [MDCO-PCS-16-01 (ORION-3)] and Phase III lipid-lowering studies [MDCO-PCS-17-03 (ORION-9), MDCO-PCS-17-04 (ORION-10), or MDCO-PCS-17-08 (ORION-11)]. Up to 3300 subjects with atherosclerotic cardiovascular disease (ASCVD), ASCVD-risk equivalents (eg, diabetes and familial hypercholesterolemia), heterozygous [REDACTED] familial hypercholesterolemia (HeFH [REDACTED]) and elevated LDL-C despite treatment with LDL-C lowering therapies who are eligible and willing to participate may be enrolled. The objectives of the study is to evaluate the efficacy, safety, and tolerability of long-term dosing of inclisiran. Informed consent will be obtained from subjects before the initiation of any study-specific procedures. The EOS visit in the previous feeder studies will be Day 1 in the extension trial except for subjects enrolled in Sweden. Sweden Specific Protocol Amendment 1 (to Global Amendment 1 version, dated 1 Nov 2018) was implemented to allow limited lab tests to be done on Day 1 and to collect any safety information during the gap between feeder's EOS and Day 1 of this study until ethics committee approval was granted in that country. Subjects moving over from the open label ORION-3 study will not receive study medication at Day 1. Their first dose of study medication in this trial will be at day 90. This is to maintain their 6 months dosing schedule on inclisiran treatment. This trial will be a global, multicenter study in approximately 300 centers.

The duration that each subject is expected to participate in this study is a maximum of 3 years or the occurrence of one of the following events, whichever occurs first:

- a recommendation of discontinuation by the investigator or Sponsor,
- a decision by the subject to discontinue for any reason,
- an administrative decision is made to end the study

3.2 Schematic Diagram of Study Design

Figure 3-1 Study Design

* Subjects from the open label ORION-3 study will receive no drug administration on Day 1

3.3 Primary Efficacy Endpoint

The primary endpoint of this study is:

Proportion of subjects who attain global lipid targets (entry criterion from respective previous study) for their level of ASCVD risk at EOS.

3.4 Secondary Efficacy Endpoints

The secondary endpoints of this study are:

- Absolute change and percentage change in LDL-C from baseline (defined as baseline in feeder study) to EOS
- Absolute change and percentage change in other lipids and lipoprotein from baseline (defined as baseline in feeder study) to EOS

3.5 Safety Endpoints

The safety endpoint of this study is:

- To evaluate the safety and tolerability profile of long-term use of inclisiran

3.6 Measures to Minimize/Avoid Bias

This is a long-term extension study. Subject enrollment will be based on completion of one of the Phase III lipid-lowering feeder studies [MDCO-PCS-17-03 (ORION-9), MDCO-PCS-17-04 (ORION-10) or MDCO-PCS-17-08 (ORION-11)] or Phase II trial [MDCO-PCS-16-01 (ORION-3)]. To minimize bias, laboratory tests related to efficacy and safety will continue to be conducted via a central laboratory.

4 Subject Population

4.1 Number of Subjects

Approximately 3300 subjects will be studied at centers globally (approximately 300 sites).

4.2 Inclusion Criteria

Subjects may be included in the study if they meet all of the following criteria:

1. Completion of a previously qualifying Phase II lipid lowering trial [MDCO-PCS-16-01 (ORION-3)] or Phase III lipid-lowering ORION feeder study [MDCO-PCS-17-03 (ORION-9), MDCO-PCS-17-04 (ORION-10), or MDCO-PCS-17-08 (ORION-11)] meaning the subject received the last dose of study drug and completed the final study visit per applicable protocol.
2. On current lipid-lowering therapies (such as a statin and/or ezetimibe) from previous study with no planned medication or dose change during study participation.
3. Willing and able to give informed consent before initiation of any study-related procedures and willing to comply with all required study procedures.

4.3 Exclusion Criteria

Subjects will be excluded from the study if any of the following exclusion criteria apply prior to entry into the study:

1. Any uncontrolled or serious disease, or any medical or surgical condition, that may either interfere with participation in the clinical study, and/or put the subject at significant risk [according to investigator's (or delegate's) judgment] if he/she participates in the clinical study.
2. An underlying known disease, or surgical, physical, or medical condition that, in the opinion of the investigator (or delegate) might interfere with interpretation of the clinical study results.
3. Severe concomitant noncardiovascular disease that carries the risk of reducing life expectancy to less than 3 years.
4. Active liver disease defined as any known current infectious, neoplastic, or metabolic pathology of the liver or unexplained alanine aminotransferase (ALT), aspartate aminotransferase (AST), elevation >3x the upper limit of normal (ULN), or total bilirubin (TBIL) elevation >2x ULN at the last recorded visit in the feeder study prior to study entry visit.
5. Females who are pregnant or nursing, or who are of childbearing potential and unwilling to use at least one method of acceptable effective contraception (eg, oral contraceptives, barrier methods, approved contraceptive implant, long-term injectable contraception, intrauterine device) for the entire duration of the study. Exemptions from this criterion:
 - a. Women >2 years postmenopausal (defined as 1 year or longer since their last menstrual period) AND more than 55 years of age
 - b. Postmenopausal women (as defined above) and less than 55 years old with a negative pregnancy test within 24 hours of enrollment
 - c. Women who are surgically sterilized at least 3 months prior to enrollment

6. Planned use of other investigational medicinal products other than inclisiran or devices during the course of the study.
7. Any condition that according to the investigator could interfere with the conduct of the study, such as but not limited to:
 - a. Subjects who are unable to communicate or to cooperate with the investigator
 - b. Unable to understand the protocol requirements, instructions and study-related restrictions, the nature, scope, and possible consequences of the study (including subjects whose cooperation is doubtful due to drug abuse or alcohol dependency)
 - c. Unlikely to comply with the protocol requirements, instructions, and study-related restrictions (eg, uncooperative attitude, inability to return for follow-up visits, and improbability of completing the study)
 - d. Have any medical or surgical condition, which in the opinion of the investigator would put the subject at increased risk from participating in the study
 - e. Persons directly involved in the conduct of the study

4.4 Withdrawal Criteria

All subjects have the right to withdraw from the study at any point during treatment without prejudice. The investigator can discontinue any subject at any time if medically necessary. It will be documented whether or not each subject completed the clinical study. If study treatment or observations were discontinued, the reason will be recorded and the Sponsor should be notified promptly. The reasons that a subject may discontinue participation in a clinical study could be from one or more of the following:

- AE(s)
- Death
- Subject withdrew consent
- Physician decision
- Lost to follow-up
- Initiation of protocol-prohibited lipid-lowering therapy (eg, an approved PCSK9 inhibitor)

The applicable reason(s) above will be recorded in the eCRF and subjects should be encouraged to complete the EOS visit. All data collected up until the time of subject withdrawal is to be entered into the electronic case report form (eCRF). Any withdrawn subjects will not be replaced in this study. No further follow-up is allowed with the subject to collect additional information following discontinuation from the trial.

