4.4.1 Individual Subject Dosing Stopping Criteria

During the study subjects will have clinic visits at regular intervals. Dosing with inclisiran should be temporarily discontinued or stopped in subjects with:

1. Intolerable AEs, or if the investigator believes that continuing dosing will be detrimental to the subject's mental or physical health. This includes severe or serious reactions at the injection site and any anaphylactic type reactions.
2. Unexplained increases in transaminases (ALT or AST) or total bilirubin as follows:
 - a. ALT or AST >8xULN

- b. ALT or AST >5xULN for more than 2 weeks
- c. ALT or AST >3xULN and (total bilirubin >2xULN or INR >1.5)
- d. ALT or AST >3xULN with the appearance of fatigue, nausea, vomiting, right upper quadrant pain or tenderness, fever, rash, and/or eosinophilia (>5%)

The investigator should evaluate to see if other causes for the laboratory abnormalities are immediately apparent, such as obstructive gall bladder or bile duct disease, viral or alcoholic hepatitis, malignancy involving the liver, congestive hepatopathy, other hepatotoxins or heritable disorders.

- 3. Unexplained creatine kinase (CK) values >5 x ULN confirmed by repeat test when the CK elevation is associated with muscle pain, muscle tenderness and/or muscle weakness, or new onset renal dysfunction.

In the case that study medication is permanently discontinued the subject will be asked to return to complete an EOS visit, which should occur at least 90 days following the last dose of inclisiran.

All subjects should be followed until all clinically significant laboratory abnormalities return to normal or to the baseline state. Subjects discontinuing the trial due to withdrawal of consent or initiation of other PSCK9 lipid lowering therapies will not be followed up within the trial.

5 Treatment of Subjects

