5.3 Medical Management Guidelines

5.3.1 Adverse events

Adverse events or abnormal test findings must be followed until the event (or its sequelae) or the abnormal test finding resolves, stabilizes at a level acceptable to the Sponsor/Investigator and/or returns to baseline values.

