5.3.2 Pregnancy

Pregnant women are excluded from the study. If a subject becomes pregnant during the course of the study, the investigational product administration must be discontinued and the pregnancy should be followed through to outcome. Follow-up information on newborns will be sought. Reporting of pregnancy and any associated AEs are specified in [Section 8.4.3.2](#).

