8.4.3.2 Pregnancy/Lactation Exposure

Occurrences of pregnancy/lactation exposure in a study subject from Day 1 through EOS must be reported to the Sponsor within 24 hours using the Pregnancy/Lactation Exposure Report Form.

In cases where a pregnancy/lactation exposure occurs with a SAE, the SAE Report Form should be used to report the SAE and the Pregnancy/Lactation Exposure Report Form should be used to report the pregnancy/lactation exposure.

When a pregnancy/lactation exposure occurs without any concurrent SAE, the Pregnancy/Lactation Exposure Report Form must be submitted alone.

The pregnancy should be followed up to determine outcome, including spontaneous or voluntary termination, details of the birth, and the presence or absence of any birth defects, congenital abnormalities, or maternal and/or newborn complications. Newborns should be followed for 12 months.

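### Protocol 4.4 bars follow-up of subjects who leave the trial early, against the duty in 4.4.1 and 5.3.1 to follow open adverse events and laboratory abnormalities

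*Protocol*

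**What the plan says.** Protocol 4.4 lists six reasons for leaving the study: adverse event, death, withdrawal of consent, physician decision, loss to follow-up, and start of a prohibited lipid-lowering therapy. It then says that "subjects should be encouraged to complete the EOS visit" and closes with a ban that exempts no reason: "No further follow-up is allowed with the subject to collect additional information following discontinuation from the trial."

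Four other sections set follow-up duties:

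- **4.4.1 (dosing stopping criteria):** "All subjects should be followed until all clinically significant laboratory abnormalities return to normal or to the baseline state." The exemption, which concerns follow-up inside the trial, is narrow: "Subjects discontinuing the trial due to withdrawal of consent or initiation of other PSCK9 lipid lowering therapies will not be followed up." For a permanent stop of drug, "In the case that study medication is permanently discontinued the subject will be asked to return to complete an EOS visit", at least 90 days after the last dose.
- **5.3.1 (adverse events):** the rule for adverse events and abnormal results is that they "must be followed until the event (or its sequelae) or the abnormal test finding resolves, stabilizes at a level acceptable to the Sponsor/Investigator"; going back to baseline also ends the duty. No reason for leaving is exempted.
- **5.3.2 (pregnancy):** if a subject becomes pregnant, "the investigational product administration must be discontinued and the pregnancy should be followed through to outcome".
- **8.4.3.2 (pregnancy reporting):** the outcome includes "birth defects, congenital abnormalities, or maternal and/or newborn complications", and newborns are to be followed for 12 months.

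Section 6.5 says that participation is complete once the EOS visit has taken place. None of these sections refers to the ban in 4.4 or says which rule prevails.

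**The concern.** Section 4.4 is where a site will look when a subject leaves, and its last sentence is a prohibition. Suppose a subject permanently stops dosing for ALT above 8xULN, then leaves the trial for that adverse event without withdrawing consent, with ALT still raised at the last visit. Sections 4.4.1 and 5.3.1 say to keep following; 4.4 says this is not allowed. The site must breach one of them.

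The first thing at stake is the subject's own safety. The second is the record of how a possible drug effect ended. Long-term safety and tolerability is one of the two primary objectives (Protocol 2.1), and 8.6.2 names drug-induced liver injury as an example of a signal that could end the study.

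**Working it through.** The plan gives no figure on this point, so the check sets the sections side by side.

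**1. Whom the ban governs.** The sentence applies after discontinuation from the trial, and it stands in a section on withdrawal that separately documents whether each subject completed. SAP 2.3.1 draws the same line between completers and early discontinuers. It counts as completers the ORION-3 rollover subjects whose time was shortened by the administrative decision only. The ban therefore concerns early discontinuers.

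**2. The reasons in 4.4, one by one, for a subject with something open at the last visit.** The ban in 4.4 applies to every row.

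| Reason in 4.4 | 4.4.1 (laboratory) | 5.3.1 (adverse events, abnormal findings) | Result |
|---|---|---|---|
| Death | – | – | Follow-up impossible |
| Lost to follow-up | – | – | Follow-up impossible |
| Consent withdrawn | Exempt | No exemption written, but follow-up cannot go on without consent | 4.4 and 4.4.1 agree |
| Adverse event | Follow | Follow | Conflict |
| Physician decision | Follow | Follow | Conflict |
| Prohibited lipid therapy: PCSK9 agent | Exempt | Follow | 4.4 agrees with 4.4.1, conflicts with 5.3.1 |
| Prohibited lipid therapy: other | Follow | Follow | Conflict |

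Counting the two lipid-therapy rows as one reason: 2 impossible + 1 in agreement + 2 in conflict + 1 split = 6.

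**3. Does the EOS visit close the gap?** Only in part. It is a single visit, at least 90 days after the last dose where the subject will return, and most events should have settled by then. Under 6.5 participation ends there. For an early discontinuer, whatever is still open is then caught between 4.4 and the other sections. The note in Section 6 also lets the visit at which a subject decides not to return serve as EOS, so that visit can come sooner.

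**4. Is there another route?** Section 8.4.1 provides for follow-up information on reported SAEs and for SAEs notified after the study period. It does not cover non-serious adverse events or laboratory abnormalities, so the gap falls mainly there.

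**5. Pregnancy.** Section 5.3.2 stops the product, not participation, so it does not collide with 4.4 directly. The conflict appears once a pregnant subject leaves the trial before the outcome is known. If the stop is permanent, 4.4.1 asks for an EOS visit and 6.5 ends participation there, which makes the case foreseeable. Maternal complications concern the subject herself, so the words of 4.4 reach them.

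**6. Effect on the analysis.** SAP 2.7.1 classes an event as treatment-emergent by its onset, so later follow-up of an open event does not change incidence. Protocol 10.2.3 excludes events that occur beyond the observational period from the planned analysis. What could change is the recorded outcome of events already counted, such as the worst outcome of injection-site events (SAP 2.7.1.1.1) or the return of liver values to baseline level (SAP 2.7.3.3).

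**The case against.** *The sections address different things.* On this view 4.4 concerns leaving the trial, and the others concern stopping the drug. This fails for 4.4.1, which itself speaks of subjects discontinuing the trial and exempts only two reasons. If the ban in 4.4 were meant to be universal, that exemption would be redundant. Section 5.3.1 carries no such limit either.

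*A site can comply by delaying EOS.* Section 4.4.1 and Table 6-1 set only a minimum of 90 days after the last dose. A willing subject with raised ALT could stay in the trial off drug, be retested, and have EOS after recovery. Meeting the ALT criterion stops dosing, perhaps temporarily; it does not remove anyone from the trial. This stands as a partial workaround, and it shows that the sections do not always collide. It does not help a subject who actually discontinues.

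*The specific pregnancy rule prevails over the general one.* Section 8.4.3.2 has its own report form, Amendment 2 added the 12-month newborn follow-up, and the newborn is not the subject named in 4.4. This is a sensible reading and the reason for treating pregnancy as secondary. The documents do not state it, however, and it leaves maternal outcomes under the ban.

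*The effect is small.* This stands.

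A reader might also infer that 4.4 blocks follow-up of anything open at EOS in any subject. The documents do not support that: a subject who completes Day 1080 has not discontinued, so 4.4 does not restrict her follow-up. Nor do they support a figure for how long after EOS a pregnancy would run, because EOS for a discontinuer has a lower bound and no fixed day.

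**Conclusion.** The contradiction is real and confined to early discontinuers. It is direct between 4.4 and both 4.4.1 and 5.3.1 for consenting subjects who leave for an adverse event, physician decision or a prohibited non-PCSK9 lipid therapy with an adverse event or clinically significant laboratory abnormality still open. For those who start another PCSK9 therapy, the laboratory rule in 4.4.1 agrees with 4.4, but 5.3.1 still does not. The pregnancy conflict is indirect.

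The documents give no count of such subjects; it is probably small. It would be tempting to say that the primary safety results are compromised. They are not: treatment-emergent incidence is unaffected, and only outcome and return-to-baseline details can move. The case for correction rests on subject safety and on clear instructions to sites. The conclusion assumes that 4.4 means what it says and that no document outside the protocol and SAP settles precedence.

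**What to change.** Replace the last sentence of 4.4 with three rules, cross-referenced from 4.4.1 so that its PCSK9 exemption is read the same way:

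1. After withdrawal of consent, there is no further follow-up of any kind.
2. After the start of another PCSK9 therapy, there are no further scheduled visits or efficacy assessments.
3. For all other early discontinuers, and for any open safety event in a subject who still consents (including those under rule 2), adverse events, clinically significant laboratory abnormalities and pregnancies are followed under 4.4.1, 5.3.1, 5.3.2 and 8.4.3.2, and the last known outcome is recorded.

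Restricting the ban only to the two reasons in 4.4.1 would not be enough. It would leave 4.4 at odds with 5.3.1 and 8.4.3.2 for a consenting subject who starts a PCSK9 therapy with something open.

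The cost is a short clarification of the protocol and a few extra contacts or repeat tests in willing subjects, which the sections named in rule 3 already call for. The SAP needs no change: an event or liver value still open at the last record stays classed as not resolved or not returned to baseline level.
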